3.5.5 SARI patients testing negative for SARS-CoV-2/influenza (test-negative controls)

A control will be defined as a hospitalised patient fulfilling the SARI case definition, with a respiratory sample negative for SARS-CoV-2 by PCR (for CVE) or a respiratory sample negative for influenza (for IVE) on admission to hospital.

It is advised that all sites test for both SARS-CoV-2 and influenza during the influenza season, as well as for all other respiratory viruses (as appropriate, depending on time of year), even if they are not participating in IVE. If this is not feasible, then during influenza season all samples that are negative for SARS-CoV-2 should also be tested for influenza (if not already tested at primary care level).

Controls that are negative by PCR but have Ct results suggestive of COVID-19⁶, and those with prior SARS-CoV-2 infection in the three months before admission, may be excluded as controls in sensitivity analyses (see Section 3.5.7 'Exclusion criteria').

- A study site/country measuring only CVE should indicate which testing strategy they will use (testing all samples for both SARS-CoV-2 and influenza, or only testing for influenza in those negative for SARS-CoV-2).
- > Each study site/country to indicate whether they can test for other respiratory viruses, only SARS-CoV-2 and influenza, or only SARS-CoV-2.

Other control groups (optional)

During periods when respiratory viruses are in low circulation, the number of SARI patients testing negative for SARS-CoV-2/influenza may be limited. Some sites may therefore wish to include other control groups, either in addition to SARI controls or as an alternative, and these must be recruited throughout the whole study period.

Examples of other control groups include:

- Patients testing PCR-negative to all respiratory viruses;
- Patients testing PCR-positive to respiratory viruses other than influenza (if IVE) or SARS-CoV-2, e.g. rhinovirus, respiratory syncytial virus (RSV), etc.; noting that patients with seasonal coronaviruses are excluded for CVE;
- Patients hospitalised with non-SARI related symptoms matched by time, age group and, if possible, underlying conditions:
 - Example source of hospitalised non-SARI cases: hospital wards admitting patients without COVID-19.
 Primary care: selection of GP patients belonging to the hospital catchment area and vaccination target
- group matched by time and age group:
 - Example source of GP patients: contact the GP for the case and select patients from his/her list (matching by GP).
- Community controls:
 - Random selection of community controls belonging to the vaccination target group, matched by time and age group (e.g. vaccine registry, telephone random survey, other planned survey);
 - Vaccination coverage in cases will be compared to vaccination coverage in the vaccination target population (screening method). Vaccination coverage should be available by time, age group and comorbidities;
 - Vaccination coverage among GP patients in the hospital catchment area: a random sample of GPs in the hospital catchment area can be used to compute the proportion of GP patients who are vaccinated
 - Vaccination coverage using vaccination centres in the hospital catchment area: the vaccination; coverage can be computed by dividing the number of individuals vaccinated (by age group, target group) by the number of individuals eligible for vaccination in the hospital catchment area (by age group, target group). Several methods can be used to estimate the population in the hospital catchment area.

All control groups should represent the vaccination coverage of the population giving rise to the cases. As the circulation of SARS-CoV-2/influenza and vaccination coverage changes over time, it is recommended that cases and controls be matched by time (e.g. onset of SARI symptoms) or adjusted by time in the analysis.

Each study site/country including other control groups should define the control group, how controls will be selected, representativeness (vaccination coverage in the population giving rise to the cases) and potential limitations.

⁶ https://www.who.int/publications/i/item/diagnostic-testing-for-sars-cov-2

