3.5.4 SARI patients confirmed as influenza

A confirmed influenza case will be defined as a hospitalised patient fulfilling the SARI case definition, with a respiratory sample PCR-positive for influenza⁵.

³ ECDC possible COVID-19 case definition: https://www.ecdc.europa.eu/en/covid-19/surveillance/case-definition

⁴ WHO SARI case definition: https://www.who.int/teams/global-influenza-programme/surveillance-and-monitoring/case-definitions-for-ili-and-sari

⁵ No requirement for the dates of the test. There are additional requirements in the exclusion criteria relating to test date and symptom onset.

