3.5.6 Exclusion criteria

The patient will not be enrolled in the study if she/he:

- is unwilling to participate or unable to communicate and give consent (the consent may also be given by her/his legal representative, or by specific consent procedures, acceptable according to the local ethical review process);
- has a contraindication for the COVID-19 (for CVE) or influenza (for IVE) vaccination;
- cannot be swabbed due to severe septum deviation, obstruction or other conditions that contra-indicate swabbing:
- has a history of hospitalisation within the 14 days immediately prior to this admission (including transfers from another hospital);
- had his/her SARI onset ≥ 48 hours after admission to the hospital (for IVE) or ≥ 7 days after admission to the hospital (for CVE);
- was institutionalised at the time of symptom onset (lives at a care-home/residence for people who require
 continual nursing care and have difficulty with the required activities of daily living);
- had a respiratory specimen taken ≥ 8 days after SARI symptom onset (for IVE) or ≥ 10 days after SARI symptom onset (for CVE);
- had a respiratory sample taken ≤ 3 days before SARI symptom onset (for CVE)
- tested positive for any influenza virus in the current season before the onset of symptoms leading to the current hospitalisation (IVE).

Information will be collected on these and other potential exclusion factors and patients will be excluded from primary analyses according to available evidence on these factors (not all available at time of writing).

In sensitivity analyses, the CVE/IVE will be estimated:

- with different cut-offs for numbers of days between onset and swabbing, onset and hospitalisation, and between vaccination and onset of symptoms;
- excluding those positive for seasonal coronaviruses (e.g. HCoV-NL63, HCoV-229E, HCoV-OC43 and HCoV-HKU1):
- excluding those who are current controls (SARS-CoV-2 negative for CVE; influenza negative for IVE) but were
 positive by PCR in the previous year before the current hospitalisation, or reported clinically confirmed COVID19, so as to determine the best cut-off period for having had a previous positive test during the preceding
 year versus 'any previous positive test' irrespective of date;
- using results from rapid antigen tests (RATs) when PCR information unavailable;
- dropping SARS-CoV-2-positive controls from IVE analysis and dropping influenza-positive controls from CVE analysis;

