3.7 Laboratory methods

Study nurses or physicians will collect respiratory specimens (see Section 4.4) from all eligible patients, respecting safety standards for COVID-19 and influenza, and following WHO biosafety guidelines.⁷

> Each study site/country to describe the type (nasopharyngeal/oropharyngeal or both) and number of swabs taken for each patient.

Influenza laboratory confirmation will be done using RT-PCR or multiplex RT-PCR. Specimens will undergo molecular analysis for currently circulating influenza viruses.

PCR should be run with the inclusion of an internal/external quality control. It is recommended that the quality of the samples be monitored using an internal control to check for the presence of human cells in respiratory specimens.

⁷ Any non-propagative diagnostics (e.g. sequencing, RT-PCR) should be conducted at a facility using procedures equivalent to biosafety level 2 (BSL-2), while propagative work (e.g. virus culture, isolation or neutralisation assays) should be conducted at a containment laboratory with inward directional airflow (BSL-3). Patient specimens from suspected or confirmed cases should be transported as UN3373, 'biological substance category B'. Viral cultures or isolates should be transported as category A, UN2814, 'infectious substance, affecting humans'[32].

ECDC's recommendation for SARS-CoV-2 laboratory confirmation is by viral RNA detection with nucleic acid amplification tests, such as RT-PCR. Specimens will undergo molecular analysis for currently circulating SARS-CoV-2 virus. During the influenza season, influenza virus tests will also be performed (and this is also recommended for countries not performing IVE), provided that there is circulation of influenza viruses in the community [30,31]. This is especially important to identify any potential association between influenza and SARS-CoV-2.

Following the procedures outlined by each study, all or a systematic sample of the detected viruses will undergo gene sequencing. The sampling procedure can include sequencing all viruses, or a systematic sample. The systematic sample should be representative of cases and be large enough to provide reasonable precision when calculating proportions of virus change over time. Guidance on random sampling for selection of samples for sequencing is provided in Annex 3.

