3.9.3 Information on swab and test results

For each patient, sites will collect information on:

- date of admission (to allow estimation of and stratification by time from onset to hospitalisation, and to measure length of hospital stay);
- date of discharge/death (to allow the length of hospital stay to be measured);
- date of swab or date sample obtained (to allow estimation of and stratification by delay from swab to onset);
- information on COVID-19/influenza test(s) performed and laboratory results:
 - type of influenza and/or COVID-19 test (PCR, rapid test)
 - result of influenza and/or COVID-19 test
 - including information on antigenic and genetic analysis, if available

Some studies will be carrying out testing for other respiratory viruses. Study sites can collect:

 test results from any other respiratory viruses (e.g. rhinovirus, RSV, enterovirus, adenovirus, human metapneumovirus, seasonal coronaviruses, etc.)

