4.2 Laboratory tests

High specificity is needed for COVID-19 confirmation. COVID-19 laboratory confirmation will be carried out using RT-PCR or multiplex RT-PCR. Influenza laboratory confirmation will be carried out using RT-PCR or by culture.

- Each study site/country to describe the tests and kits used for COVID-19 and influenza; and, if necessary, other respiratory virus detection.
- Each study site/country to specify sequencing methods.

PCR should include an internal/external quality control. It is advisable to monitor the quality of the respiratory samples by checking for presence of cells in the specimens. In addition, quality assurance of assay performance at sites should be evaluated by participating in External Quality Assessment Programmes (EQAS).

- > Each study site/country to describe quality controls for specimens.
- Each study site/country to describe genetic and antigenic analyses.

5. Limitations

With any multi-centre study, there is always the potential for heterogeneity across study sites. In addition, during a pandemic with such high caseloads for hospitals, there may be difficulties in collecting all data, and not all cases included will have laboratory confirmation. There is also the possibility that very severely ill patients (e.g. those who are ≥80 years old, or who are extremely frail and/or in nursing homes) may not be admitted to hospital at all, and would be missed by the study. For both influenza and COVID-19, there is symptom variability across age groups (e.g. less fever seen in the elderly). Potential limitations to the CVE/IVE estimates are discussed below.

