viruses)	lab_fluany	Numeric (categorical)	0 = Negative	Laboratory result: any influenza virus type
			1 = Positive	
			2 = Not done	
			8 = Do not know	
	lab_flu_type	Numeric (categorical)	1 = influenza A(H1N1)	If positive for influenza, indicate which type and subtype, if known
			2 = influenza A(H3N2)	type and subtype, ii known
			3 = influenza A (untyped)	
			4 = influenza B/Yamagata	
			5 = influenza B/Victoria	
			6 = influenza B (untyped)	
			8 = Do not know	
	lab_mers	Numeric (categorical)	0 = Negative	Laboratory result: MERS-CoV

	Variable	Туре	Values and coding	Definition
			1 = Positive	
			2 = Not done	
			8 = Do not know	
	lab_othcov	Numeric (categorical)	0 = Negative	Laboratory result: other coronavirus
			1 = Positive	
			2 = Not done	
			8 = Do not know	
	lab_rsv	Numeric (categorical)	0 = Negative	Laboratory result: RSV
			1 = Positive	
			2 = Not done	
			8 = Do not know	
	lab_metap	Numeric (categorical)	0 = Negative	Laboratory result: metapneumovirus
			1 = Positive	
			2 = Not done	
			8 = Do not know	
	lab_adeno	Numeric (categorical)	0 = Negative	Laboratory result: adenovirus
			1 = Positive	
			2 = Not done	
			8 = Do not know	
	resp_path	Numeric (categorical)	0 = Negative	Other respiratory pathogen patient
			1 = Positive	tests positive for
			2 = Not done	
			8 = Do not know	
	resp_path_oth	Text		Specify other respiratory pathogen
Section B Patient information/	dob	Date	dd/mm/yyyy	Date of birth (only if no age) (optional)
characteristics	ethnic	Numeric (categorical)		Patient's ethic group (note: codes will be country-specific) (optional)
Optional variables	ethnic_sp	Text		Other ethnic group not specified in coding above (optional)
	essential_worker	Numeric (categorical)	0 = No	Whether the patient is any other type of essential worker with much human
			1 = Yes	contact (e.g. teacher, police person,
			8 = Do not know	supermarket worker) (optional)
	esswork_sp	Text		Specify which other type of essential worker (optional)
	occupation	Text		Patient's occupation, if not already captured (note: this may be collected another way, e.g. by national occupational code, depending on country) (optional)
	height	Numeric (integer)		Height of patient in metres (optional)
	weight	Numeric (integer)		Weight of patient in kg (optional)
	ses	Numeric (categorical)		Indicate results from socioeconomic or deprivation index used (optional)
Section B	trimester	Numeric (categorical)	1 = first trimester	If patient is pregnant, indicate which

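### Section 3.5.5 names no influenza test method for IVE controls, section 4.2 conflicts with 3.5.4 and 3.7, and Annex 1 lacks the influenza test-type and earlier-positive fields that stated IVE analyses need

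*Protocol*

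**What the plan says.** **Cases and controls.** Section 3.5.4 defines an influenza case as a SARI patient "with a respiratory sample PCR-positive for influenza". Section 3.5.5 defines the control by "a respiratory sample negative for SARS-CoV-2 by PCR (for CVE) or a respiratory sample negative for influenza (for IVE) on admission to hospital". PCR qualifies the SARS-CoV-2 arm of that sentence only.

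**Laboratory method.** Section 3.7 has specimens taken from all eligible patients and states: "Influenza laboratory confirmation will be done using RT-PCR or multiplex RT-PCR". Section 4.2 states: "Influenza laboratory confirmation will be carried out using RT-PCR or by culture".

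**Data to be collected.** Section 3.9.3 says that sites will record, for each patient, the "type of influenza and/or COVID-19 test (PCR, rapid test"). Section 3.9.9 asks each site to collect and describe a measure of prior SARS-CoV-2/influenza infection, but the items it lists concern SARS-CoV-2 only.

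**Minimum dataset.** Annex 1 holds a test-type field for SARS-CoV-2 (`lab_covtesttype`, Section J) and earlier-positive fields for it (`prev_labcovid`, with type and date, Section I). For influenza, Section K holds the swab date (`swabdate_flu`), the result (`lab_fluany`, defined as "Laboratory result: any influenza virus type") and the virus type or subtype (`lab_flu_type`).

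**Rules that need more than this.** Section 3.5.6 excludes from IVE anyone who "tested positive for any influenza virus in the current season before the onset of symptoms leading to the current hospitalisation (IVE"). It also lists sensitivity analyses "using results from rapid antigen tests (RATs) when PCR information unavailable" and excluding current controls, influenza-negative ones included, who had an earlier positive PCR. Section 2.2, section 5.1.5 and the stratified analyses in Annex 2 also use prior influenza infection.

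**The concern.** A test-negative design depends on cases and controls being separated by the same test. Here the case definition names PCR, the IVE control definition names nothing, and the two laboratory sections disagree on the permitted method. Section 3.9.3 foresees rapid influenza tests, so some negatives could rest on a rapid result.

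An influenza patient missed by a less sensitive test becomes a control and brings case-like vaccine coverage into the control group. That pulls IVE down, more so at sites with more rapid testing, and so could also look like heterogeneity between sites.

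The pooled analysis could guard against this if it knew how each patient was tested, but the minimum dataset does not carry that variable. The same gap affects earlier influenza: a primary-analysis exclusion, sensitivity analyses and an effect-modifier objective all rely on information with no influenza field. Patient-level data that are not collected cannot be recovered by a later analysis plan.

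**Working it through.** The plan states no figure on this point, so the check sets the text side by side and then illustrates the possible bias.

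**1. Field check of Annex 1**

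| Item | SARS-CoV-2 | Influenza |
|---|---|---|
| Test result in hospital | `lab_covid` | `lab_fluany` |
| Test method | `lab_covtesttype` | none |
| Earlier positive | `prev_labcovid` | none |
| Type and date of earlier positive | `prev_labcovid_type`, `prev_labcovid_date` | none |

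`lab_flu_type` is the virus type or subtype, not the test method. The optional variables at the end of the annex add no influenza test field.

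**2. Which stated steps these fields serve**

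| Stated step | Field needed | In Annex 1? |
|---|---|---|
| Confirm that IVE controls are PCR-negative (3.7) | influenza test type | no |
| Rapid-antigen sensitivity analysis for IVE (3.5.6) | influenza test type | no |
| Exclude earlier influenza positives in the season (3.5.6) | earlier positive, date | no |
| Exclude controls with an earlier positive PCR (3.5.6) | earlier positive, date, type | no |
| Prior influenza as effect modifier or stratum (2.2, Annex 2) | earlier positive | no |

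**3. Possible bias**

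All inputs are assumptions, because the documents give none: coverage in true non-influenza patients c = 50%; influenza in π = 10% to 30% of SARI patients; share tested by rapid test only f = 10% to 100%; rapid-test sensitivity Se = 50% to 90%; PCR sensitivity 100%; no false positives; misses unrelated to vaccination; cases counted by PCR only.

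- Case coverage: p1 = o/(1 + o), where o = OR × c/(1 − c)
- False-negative controls: FN = f × π × (1 − Se)
- True-negative controls: TN = 1 − π
- Coverage in the contaminated controls: c* = (FN × p1 + TN × c)/(FN + TN)
- Observed IVE = 1 − o / [c*/(1 − c*)]

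Worst corner, true IVE 50% (OR = 0.5, o = 0.5, p1 = 0.333) with π = 0.3, f = 1, Se = 0.5:

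- FN = 1 × 0.3 × 0.5 = 0.15 and TN = 0.70, so false negatives are 0.15/0.85 = 17.6% of controls
- c* = (0.15 × 0.333 + 0.70 × 0.5)/0.85 = 0.40/0.85 = 0.4706, odds 0.889
- Observed OR = 0.5/0.889 = 0.5625, so IVE reads 43.8%

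Other points, true IVE 50%, π = 0.2, Se = 0.7:

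| Rapid-only share f | False-negative controls | Observed IVE |
|---|---|---|
| 10% | 0.7% | 49.8% |
| 50% | 3.6% | 48.8% |
| 100% | 7.0% | 47.6% |

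Over the whole grid, observed IVE runs from 43.8% to 50.0% for a true 50%, from 25.5% to 30.0% for a true 30%, and from 63.7% to 70.0% for a true 70%. The shift is never upwards.

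**The case against.** A reader might infer from 3.5.5 that IVE controls may be enrolled without PCR. The document does not support that. Section 3.7 takes specimens from all eligible patients and specifies RT-PCR for influenza, and 3.5.6 uses rapid antigen results only in a sensitivity analysis when PCR is missing. PCR for everyone is the evident intent, and the missing words in 3.5.5 are a drafting lapse. What stands is that the operative control definition is silent, that 3.7 speaks of confirming influenza rather than of defining a negative, and that 4.2 gives a different rule.

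A reader might also take the mention of primary-care testing in 3.5.5 as widening the control definition. It belongs to a fallback for sites that cannot test every sample for both viruses; the control itself needs a sample on admission.

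A third tempting reading is that the exclusions cannot be applied at all. That is too absolute. The earlier-influenza rule is also an enrolment exclusion that sites can apply before pooling. Sections 3.9.3 and 3.9.9 ask sites for the information, Annex 1 is a minimum that sites may modify, and Annex 5 has sites describe their kits and rapid-test use. These routes are real, but none gives the pooled dataset a uniform patient-level field. The allowance in 3.11.1 for site-specific coding does not oblige a site to send a variable that the annex omits.

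Finally, larger biases can be produced. With 40% influenza among SARI patients, sensitivity of 50% to 70% and a site that never uses PCR on its negatives, a true IVE of 60% would read 50% to 54%. Nothing in the protocol describes such a site, and under 3.7 the intended share of non-PCR controls is zero.

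**Conclusion.** The point holds as an inconsistency and a dataset gap. Section 3.5.5 does not name the influenza test for controls, 4.2 disagrees with 3.5.4 and 3.7, and Annex 1 does not carry the influenza test type promised in 3.9.3 or any earlier influenza result. The steps in the second table therefore cannot be carried out or verified from the Annex 1 variables alone.

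The direction of any resulting bias is downwards on IVE, given that misses do not depend on vaccination. Its size is unknown, because the documents give no share of non-PCR testing. Under the assumed ranges it is about 0 to 6 points for a true IVE of 50%, and it is small unless rapid-only testing is common. The gaps in the prior-influenza analyses do not depend on the size of that bias.

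**What to change.** - In 3.5.5, state that IVE controls are negative for influenza by PCR.
- Reconcile the influenza method in 4.2 with 3.5.4 and 3.7.
- In Annex 1, Section K, add an influenza test-type field with PCR, rapid test, culture, other and unknown as values, on the model of `lab_covtesttype`.
- In Annex 1, add earlier-influenza-positive fields on the model of Section I: result and date, with test type where available. The type matters for the sensitivity analysis in 3.5.6, which concerns earlier PCR positives.
- Restrict the primary IVE to PCR results, and keep rapid-only results for the sensitivity analysis already listed.

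The cost is one phrase, one reconciled sentence and about four fields. Most of the information is already asked for in 3.9.3, 3.5.6 and 3.9.9; the type of an earlier influenza test is new, hence only where available. Patients with only a rapid negative leave the primary IVE, which costs some controls at sites that rely on rapid tests. Prior influenza will remain incompletely ascertained, as 5.1.5 acknowledges, so the new fields make those analyses possible but not complete.
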